12.3.2 Change in satisfaction of hair coverage quality as reported by patient

The patient satisfaction hair coverage quality questionnaire will be assessed by the patient. For each of the 7 questions, the patient might select one of the five numeric choices representing "very dissatisfied" (1) to "very satisfied" (5). Missing data will not be imputed.

A similar analysis approach as outlined for the change in satisfaction of hair coverage secondary efficacy endpoint (refer to Section 12.2.3) will be used for the change in satisfaction of hair coverage quality total score. No supportive and subgroup analyses will be performed for this endpoint.

12.4 Other Efficacy Endpoint Analyses

12.4.1 Responder Analysis: Proportion of patients achieving at least 80% in relative change from Baseline in SALT score at Weeks 4, 8, 12, 16, 20, and 24

The proportion of patients achieving at least 80% in relative change from Baseline in SALT score at Weeks 4, 8, 12, 16, 20, and 24, frequency and proportion will be summarized and analyzed similarly to the proportion of patients achieving at least a 90%, 75%, and 50% relative change from Baseline in SALT score at Weeks 4, 8, 12, 16, 20, and 24 (refer to Section 12.2.1).

12.4.2 Proportion of Subjects with a SALT Score ≤ 10 and ≤ 20 at Weeks 12 and 24

The number and percentage of subjects with a SALT score ≤ 10 and ≤ 20 at Weeks 12 and 24 will be summarized based on the mITT analysis population by visit and dosing regimen. The difference in percentages along with the two-sided Wald 90% CI will also be provided at each visit.

No supportive and subgroup analyses will be performed for this endpoint.

12.4.3 Global Impression Scales

The global impression scales employ a Likert scale measuring either disease severity or improvement after treatment. In this study, the global impression scales of severity and improvement will be performed by both the clinician and patient. The global impression scale of severity should consider the condition of the patient at the time of the assessment while the global impression scale of improvement should consider the condition of the patient at the time of the assessment compared to Baseline.

Clinical Global Impression of Severity (CGI-S)

The CGI-S will be assessed by the Investigator and will consider the severity of the patient's alopecia areata at the time of assessment. The Investigator may select one of the five numeric choices representing "Extremely severe" to "Not at all severe". Missing data will not be imputed.

	STATISTICAL ANALYSIS PLAN, Final v1.0
Protocol Number CP543.2003	Sponsor: Concert Pharmaceuticals, Inc.

Frequency and percentages will be presented by category and visit based on the mITT analysis population for each dosing regimen. No statistical inferences will be performed for this endpoint.

No supportive analyses will be performed for this endpoint. Subgroup analyses by Baseline alopecia areata subtype will be provided.

Clinical Global Impression of Improvement (CGI-I)

The CGI-I will be assessed by the Investigator and will consider the Investigator's perceived change of the patient's alopecia areata at the time of assessment compared to Baseline. The Investigator may select one of the seven numeric choices representing "Very much worse" to "Very much improved". Missing data will not be imputed.

Frequency and percentages will be presented by category and visit based on the mITT analysis population for each dosing regimen. The distribution of each treatment group across the different CGI-I categories will be compared using a Chi-square test.

Subjects will be further categorized at each visit as improved/not-improved in view of their response to the CGI-I. Improved subjects will be those who answered very much/much improved while not-improved subjects will be those who answered much worse or very much worse. Subjects with a missing value in CGI-I at a specific visit will be excluded from the analysis for that visit. Frequency and percentages will be presented by category and visit based on the mITT analysis population for each dosing regimen. The distribution of each treatment group across the different CGI-I categories will be compared using a Chi-square test.

No supportive analyses will be performed for these endpoints. Subgroup analyses by Baseline alopecia areata subtype will be provided.

Patient Global Impression of Severity (PGI-S)

The PGI-S will be assessed by the patient and will consider the severity of his/her alopecia areata at the time of assessment. The patient may select one of the five numeric choices representing "Extremely severe" to "Not at all severe". Missing data will not be imputed.

Frequency and percentages will be presented by category and visit based on the mITT analysis population for each dosing regimen. No statistical inferences will be performed for this endpoint.

No supportive analyses will be performed for this endpoint. Subgroup analyses by Baseline alopecia areata subtype will be provided.

	STATISTICAL ANALYSIS PLAN, Final v1.0
Protocol Number CP543.2003	Sponsor: Concert Pharmaceuticals, Inc.

Patient Global Impression of Improvement (PGI-I)

The PGI-I will be assessed by the patient and will consider the his/her perceived change of the patient's alopecia areata at the time of assessment compared to Baseline. The patient may select one of the seven numeric choices representing "Very much worse" to "Very much improved". Missing data will not be imputed.

Frequency and percentages will be presented by category and visit based on the mITT analysis population for each dosing regimen. The distribution of each treatment group across the different PGI-I categories will be compared using a Chi-square test.

Subjects will be further categorized at each visit as improved/not-improved in view of their response to the PGI-I. Improved subjects will be those who answered very much/much improve while not-improved subjects will be those who answered much worse or very much worse. Subjects with a missing value in PGI-I at a specific visit will be excluded from the analysis for that visit. Frequency and percentages will be presented by category and visit based on the mITT analysis population for each dosing regimen. The distribution of each treatment group across the different PGI-I categories will be compared using a Chi-square test.

No supportive analyses will be performed for these endpoints. Subgroup analyses by Baseline alopecia areata subtype will be provided.

	STATISTICAL ANALYSIS PLAN, Final v1.0
Protocol Number CP543.2003	Sponsor: Concert Pharmaceuticals, Inc.

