3 STUDY DESIGN

3.1 Overall Design

This is a randomized, parallel-group, multicenter study to evaluate the efficacy and tolerability of two dosing regimens of CTP-543 (12 mg twice daily [BID] vs 24 mg once daily [QD]) in adult patients with chronic, moderate to severe alopecia areata. Patients will be between 18 and 65 years of age and experiencing an episode of alopecia areata lasting at least 6 months and not exceeding 10 years, with at least 50% hair loss as measured by the Severity of Alopecia Tool (SALT) at Screening and Baseline, and are not concurrently being treated for alopecia areata with other treatments that might affect hair regrowth or immune response. Up to approximately 75% of alopecia areata patients with alopecia totalis or universalis, and no more than 10% of patients with alopecia ophiasis will be enrolled.

A full list of the inclusion and exclusion criteria can be found in Sections 7.1 and 7.2 in the CP543.2003 Protocol.

Patients may be screened up to 28 days prior to initiation of study drug. The Treatment Period is a 24-week dosing period where patients will be randomized to receive either 12 mg BID or 24 mg OD of CTP-543.

[figure not shown]
[figure not shown]

Figure 1: Study Design

Patients will provide informed consent prior to completing any screening procedures. Patients meeting screening criteria will continue to the Day 1 Randomization Visit for review of eligibility and Baseline assessments. Patients meeting all eligibility criteria will be randomized to receive either 12 mg BID CTP-543 or 24 mg QD CTP-543 in a 1:1 ratio. Approximately 60 patients are planned to be randomized in the study (i.e., approximately 30 patients per dosing regimen).

Patients will take the first dose of study drug in the clinic on Day 1 and will be instructed to take study drug every 12 hours. To minimize the bias in the evaluation of study endpoints, patients, investigators, and site personnel will be unaware of the active drug dosing regimen by administering 2 x 12 mg tablets and 2 x placebo tablets 12 hours apart from each other for the 24 mg QD study drug. Patients should dose study drug in the clinic on all Study Visit Days after clinical laboratory blood draws are completed.

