3.3 Randomization, Replacement, and Unblinding Procedures

Patients meeting all inclusion criteria and none of the exclusion criteria will be randomized to 12 mg BID CTP-543 or 24 mg QD CTP-543 in a 1:1 ratio. Randomization will be stratified by classification of alopecia areata subtype into one of the following three categories: 1) alopecia areata, 2) alopecia totalis or alopecia universalis, or 3) alopecia ophiasis.

Patients who withdraw or are withdrawn from the study will not be replaced.

To maintain the blind for investigators, subjects, and site personnel, subjects will take their randomized treatment in the am and pm no matter which regimen they are randomized to. The Clinical Research Organization (CRO) study team will also remain blinded to the dosing regimen until database lock.

The study will be unblinded after approval of the SAP, clinical trial data are entered into the database, any discrepancies in the data are resolved, determination of the inclusion/exclusion of each subject from each analysis population and lock of the database.

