6 STATISTICAL CONSIDERATIONS

6.1 Sample Size

A sample size of 25 patients (completers) per group provides adequate precision for the estimated dosing regimen difference for relative change in SALT score from Baseline at Week 24. Precision of the estimated difference is quantified by the width of the 90% confidence intervals (CI) for the dosing regimen difference.

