6.4 Statistical Tests

No formal hypothesis tests will be conducted. Only two-sided confidence intervals (CIs) at the 90% coverage will be presented. Nominal p-values will be provided.

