Proportion of subjects with a SALT score of ≤ 10 and ≤ 20 , at Weeks 12, and 24	Week 12, and 24	Count and proportion of subjects by visit and dosing regimen for each definition separately with difference in proportions and two-sided Wald 90% CI for each post-baseline visit
		 Main analysis: using LOCF imputation based on mITT analysis population
		 No supportive and subgroup analyses
Proportion of subjects in each CGI-S category at Baseline and Weeks 8, 12,	Baseline and Weeks 8, 12, and 24	Count and proportion of subjects by category, visit, and dosing regimen • Main analysis : with no imputation based on mITT analysis population • No supportive analyses
and 24		 Subgroup analyses: based on mITT analysis population within each subtype of alopecia areata at Baseline
Proportion of subjects in	Weeks 8, 12, and 24	Count and proportion of subjects by category, visit, and dosing regimen
each CGI-I category at Weeks 8, 12, and 24		 Main analysis: with no imputation based on mITT analysis population; distribution of each treatment group across the different categories will be compared using a Chi-square test
		 Additional analysis: Improved vs not improved at each post-baseline visit based on mITT analysis population; subjects with a missing CGI-I at a specific visit will be classified as not improved for that visit and distribution of each treatment group across the different categories will be compared using a Chi-square test at each visit.
		No supportive analyses
		Subgroup analyses: using LOCF imputation based on mITT analysis population within each subtype of alopecia areata at Baseline

	STATISTICAL ANALYSIS PLAN, Final v1.0
Protocol Number CP543.2003	Sponsor: Concert Pharmaceuticals, Inc.

Efficacy Endpoint	Collection Time	Method
Proportion of subjects in each PGI-S category at Baseline and Weeks 8, 12, and 24	Baseline and Weeks 8, 12, and 24	Count and proportion of subjects by category, visit, and dosing regimen • Main analysis: with no imputation based on mITT analysis population • No supportive analyses
and 24		 Subgroup analyses: using LOCF imputation based on mITT analysis population within each subtype of alopecia areata at Baseline

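### The seven-level CGI-I and PGI-I comparison uses a Chi-square test that ignores the order of the ratings and gives no effect estimate; a rank-based estimate with a 90% CI would be more sensitive to an ordered shift.

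*SAP*

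**What the plan says.** For each improvement scale the rater picks "one of the seven numeric choices representing" the range from worst to best (SAP 12.4.3). Protocol 16.4.1 and 16.4.2 list the levels in order, 1 being the most improved and 7 the most worsened.

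For CGI-I: "The distribution of each treatment group across the different CGI-I categories will be compared using a Chi-square test". For PGI-I: "The distribution of each treatment group across the different PGI-I categories will be compared using a Chi-square test". The CGI-I and PGI-I rows of SAP 12.5 repeat it: "distribution of each treatment group across the different categories will be compared using a Chi-square test". No ordinal or exact version, pooling of levels or rule for small expected counts is given. Missing ratings are not imputed in this main comparison.

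On size, SAP 3.1 states "Approximately 60 patients are planned to be randomized in the study (i.e., approximately 30 patients per dosing regimen", and SAP 6.1 states "A sample size of 25 patients (completers) per group provides adequate precision".

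On inference, SAP 6.4 states: "No formal hypothesis tests will be conducted. Only two-sided confidence intervals (CIs) at the 90% coverage will be presented. Nominal p-values will be provided". Protocol 11.4 likewise describes efficacy comparisons as being for estimation.

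**The concern.** A Pearson Chi-square treats the levels as unordered labels. Its value does not change if the levels are shuffled, so it cannot tell a consistent move towards improvement from scatter. It spends up to 6 degrees of freedom on a question that an ordered test answers with one.

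It also returns only a p-value. The SALT and eyebrow VAS comparisons (SAP 12.1, 12.2.1, 12.3.1, 12.4.2) each come with a between-regimen difference and a 90% CI. The two global improvement ratings do not, which sits badly with the estimation purpose in Protocol 11.4 and SAP 6.4. At stake is whether the clinician and patient ratings at Weeks 8, 12 and 24 can say anything useful about once-daily against twice-daily dosing.

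**Working it through.** The plan states no power, significance level or effect size for these scales, so there is no figure of its own to reproduce. From the documents: seven ordered levels, 1:1 allocation, about 30 randomised and 25 completers per arm, 90% CIs. Assumed: the category distributions and the odds ratios. Both 0.05 and 0.10 (the level matching a 90% CI) were examined.

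**1. Sparsity.** With equal arms, the expected count in a cell is the column total divided by 2, so a count of 5 needs a column total of at least 10. If all seven levels occur and *k* columns reach 10, then 10*k* + (7 − *k*) ≤ *N*, that is 9*k* ≤ *N* − 7.
- 30 per arm, *N* = 60: *k* ≤ 53/9, so *k* = 5. At least 2/7 = 29% of cells fall below 5.
- 25 per arm, *N* = 50: *k* ≤ 43/9, so *k* = 4. At least 3/7 = 43% fall below 5.

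**2. An invented example, 30 per arm.** Counts from level 1 to level 7: BID 10, 8, 5, 4, 1, 1, 1; QD 4, 6, 6, 8, 3, 2, 1. With equal arms, X² = Σ (BID − QD)² / column total = 36/14 + 4/14 + 1/11 + 16/12 + 4/4 + 1/3 + 0 = 5.61 on 6 df, p = 0.47, whatever order the levels are put in. The Mann-Whitney probability (BID better, ties one half) is 596/900 = 0.66, and the Wilcoxon p is 0.028.

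**3. Type I error.** In simulation (100,000 trials per setting, 25 and 30 per arm, five assumed distributions) the Chi-square rejected in 3.3-5.0% of null trials at nominal 0.05 and in 7.7-10.3% at 0.10.

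**4. Power under proportional-odds shifts**, Pearson Chi-square on occupied levels against tie-corrected Wilcoxon, 30 per arm:

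| Assumed distribution | OR | At 0.05 | Ratio | At 0.10 | Ratio |
|---|---|---|---|---|---|
| Seven levels (.20, .20, .20, .25, .07, .05, .03) | 2 | 13% v 32% | 0.40 | 23% v 44% | 0.52 |
| | 3 | 33% v 65% | 0.50 | 47% v 76% | 0.62 |
| | 4 | 52% v 83% | 0.62 | 67% v 90% | 0.74 |
| Five levels (.30, .25, .20, .20, .05) | 2 | 16% v 31% | 0.54 | 27% v 43% | 0.63 |
| | 3 | 39% v 62% | 0.62 | 53% v 74% | 0.72 |
| Four levels (.35, .25, .20, .20) | 2 | 19% v 30% | 0.64 | 30% v 43% | 0.71 |
| | 3 | 43% v 61% | 0.71 | 57% v 73% | 0.78 |

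Across the assumed seven-level distributions at OR 3 and 30 per arm, power is 32-34% v 63-66% at 0.05 and 46-49% v 74-77% at 0.10. Over all settings (OR 1.5 to 6, 25 and 30 per arm) the ratio runs from about 0.4 to about 0.9.

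**5. Check without a category distribution.** Give both tests the same noncentrality, λ = (z for 1 − α/2 + z for power)². At α = 0.05 and 50% power for a 1-df test, λ = 1.96² = 3.84, and a 6-df Chi-square has 26% power. At 80%, λ = (1.96 + 0.84)² = 7.84, and it has 52%. At α = 0.10 the figures are 29% and 54%.

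**6. Ophiasis.** Enrolment is capped at 10%, so about 0.10 × 60 = 6 patients. If they split 3 and 3 and all six ratings differ, X² = 6 on 5 df, p = 0.31, even when the arms are perfectly separated and for every other arrangement of those ratings.

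**The case against.** The strongest defence is that little rests on this p-value. CGI-I and PGI-I are in the SAP's lowest efficacy tier (12.4), are absent from the endpoint list in Protocol 11.2.1, carry nominal p-values, and have their category counts reported in any case. The SAP sets out to compare distributions, and a Chi-square does that. It can also win: in one assumed non-monotone pattern it had 23-29% power where the Wilcoxon had 7%. All of this stands. It limits the importance and makes the choice of test a trade-off, but it does not supply the missing estimate.

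Some stronger readings are tempting but not supported:

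- A reader might infer that the sparse table makes the test invalid. A rule of thumb on expected counts is broken, but the simulated type I error is at or a little below nominal.
- A reader might infer that the p-values miss a stated level. The plan states none for these tests.
- A reader might infer that the Chi-square always has less than half the power. That occurs only at 0.05, with seven levels in use and odds ratios up to about 3. At 0.10, with larger effects, or with four or five levels in use, the ratio was above one half.
- A reader might infer that this is the only comparison of these ratings. SAP 12.4.3 also plans an improved/not-improved Chi-square. As defined there, it places the three middle levels in neither group, so only the seven-level comparison uses every rating.
- A reader might infer that the SAP requires the test within ophiasis. It promises subgroup analyses by subtype but names no test for them.

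**Conclusion.** The point holds as a question of sensitivity and reporting. That the test ignores the order, and that no estimate or interval accompanies it, follows directly from the SAP. The 29% and 43% bounds are arithmetic and apply if all seven levels occur. The power loss, to roughly 0.4 to 0.9 of a rank test's power, depends on assumed proportional-odds shifts, assumed category distributions and the nominal level chosen, because the documents give none of these. The consequence is missed or unquantified differences, not false positives. No primary or secondary conclusion depends on it. Importance is low to moderate.

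**What to change.** In SAP 12.4.3 and the CGI-I and PGI-I rows of 12.5, replace the seven-level Chi-square with the Mann-Whitney probability that a patient on one regimen has a better rating than a patient on the other. Count ties as one half, give a two-sided 90% CI and name the interval method. If a nominal p-value is kept, use the Wilcoxon rank-sum test, or the CMH row-mean-score test stratified by subtype. The stratified option also needs a line in SAP 6.8, which currently plans no covariate adjustment. In the ophiasis subgroup, show counts only and say so.

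The cost is a few lines of SAP text and a small programming change, with no new data. A rank comparison is less sensitive to a non-monotone difference; the category counts already planned would still show one.

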6.3 Handling of Dropouts or Missing data

See Appendix 3 for handling of completely or partially missing dates for prior and concomitant medications and AEs. Imputed AE onset and end dates/medication start and stop dates will only be used for the determination of the treatment-emergent/concomitant status. That is, they will not be used to compute any study day or duration and will not be presented in the by-patient data listings.

For the SALT endpoints (e.g., absolute and percent changes from baseline as well as achieving at least 50%, 75%, 80%, and 90% reduction and having a SALT score ≤ 10 and ≤ 20, the Last Observation Carried Forward (LOCF) approach will be implemented for missing SALT score data, e.g., if the SALT score in the Week 16 visit window is missing, the next and closest available ontreatment SALT score measurement before the Week 16 visit window will be used for all remaining SALT assessments: Week 16, Week 20 and Week 24. Missing baseline values will not be carried forward. If a SALT assessment is missing between two non-missing SALT assessments visits, the SALT score at that visit will be interpolated using the mean of the closest pre- and post-assessments.

All other missing efficacy data as well as missing safety data will not be imputed.

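### The improved/not-improved split of CGI-I and PGI-I leaves three of the seven answers in neither group, and the SAP summary table contradicts the text on missing ratings

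*SAP*

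**What the plan says.** Protocol 16.4.1 and 16.4.2 give CGI-I and PGI-I the same seven answers: 1 very much improved, 2 much improved, 3 minimally improved, 4 no change, 5 minimally worse, 6 much worse, 7 very much worse.

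SAP 12.4.3 tabulates all seven by visit, with a chi-square test. It then forms two groups at each visit and tests those by chi-square as well. For CGI-I: "Improved subjects will be those who answered very much/much improved while not-improved subjects will be those who answered much worse or very much worse". The PGI-I paragraph has the same split, again stating that "not-improved subjects will be those who answered much worse or very much worse".

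On missing ratings, 12.4.3 says for CGI-I "Subjects with a missing value in CGI-I at a specific visit will be excluded from the analysis for that visit" and for PGI-I "Subjects with a missing value in PGI-I at a specific visit will be excluded from the analysis for that visit". For each scale it adds "Missing data will not be imputed". SAP 6.3 reserves LOCF for SALT and continues: "All other missing efficacy data as well as missing safety data will not be imputed".

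The table in SAP 12.5 describes the same additional analysis ("Improved vs not improved at each post-baseline visit based on mITT analysis population") but says "subjects with a missing CGI-I at a specific visit will be classified as not improved for that visit". The PGI-I row repeats that sentence, still naming CGI-I. The table also specifies LOCF for the subgroup entries of CGI-I, PGI-S and PGI-I, but not for CGI-S.

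**The concern.** A two-way split should give every graded patient a place. Here a patient rated no change, who is not improved in any ordinary sense, belongs to neither group. A programmer who follows the text compares marked improvers with marked worseners and leaves out everyone between.

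The missing-rating rules cannot both be programmed. SAP 5.4 summarizes early termination assessments as a separate visit, so a patient who drops out has no Week 24 rating. That patient is left out under 12.4.3 and counted as not improved under 12.5. Read literally, the PGI-I row gives no rule for a missing PGI-I at all.

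What is at stake is a dichotomy that can be built in several ways after the data are seen, on two scales, at Weeks 8, 12 and 24, and again within each subtype.

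**Working it through.** **Step 1. Place the seven answers.** Levels 1 and 2 are improved; levels 6 and 7 are not improved; levels 3, 4 and 5 are unassigned. No other section of the SAP places them, and table 12.5 gives no definition of its own.

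**Step 2. Set the missing-rating rules side by side.**

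| Place | Rule |
|---|---|
| SAP 6.3 | non-SALT efficacy data not imputed |
| SAP 12.4.3, CGI-I and PGI-I | not imputed; excluded at that visit |
| SAP 12.5, CGI-I row | missing CGI-I counted as not improved |
| SAP 12.5, PGI-I row | missing *CGI-I* counted as not improved |
| SAP 12.5, subgroup entries for CGI-I, PGI-S, PGI-I | LOCF |
| SAP 12.5, subgroup entry for CGI-S | no LOCF |

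Sections 6.3 and 12.4.3 agree with each other; 12.5 departs from both. PGI-S has no improved/not-improved split, so only its LOCF wording is at issue.

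**Step 3. Illustrate the size.** The plan gives no expected distribution of ratings, so there is no planned figure to reproduce and all counts below are assumptions. The arm size of 25 graded borrows the completer figure in SAP 6.1. Assumed: BID 15 improved, 9 at levels 3 to 5, 1 much worse; QD 9, 15 and 1. For the readings that use missing ratings I add 5 per arm, the planning allowance 30 − 25.

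The statistic is the uncorrected Pearson chi-square on 1 df, X² = N(ad − bc)² / (product of the four margins).

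- (a) 12.4.3 as written, [15, 1; 9, 1]: X² = 26 × 6² / (16 × 10 × 24 × 2) = 0.122, p = 0.73. Smallest expected cell 10 × 2 / 26 = 0.77. Omitted: 9 + 15 = 24 of 50 graded patients (48%).
- (b) The same groups with the 12.5 missing rule, [15, 6; 9, 6]: X² = 36 × 36² / (21 × 15 × 24 × 12) = 0.514, p = 0.47.
- (c) Levels 3 to 7 not improved, missing excluded, [15, 10; 9, 16]: X² = 50 × 150² / (25 × 25 × 24 × 26) = 2.885, p = 0.089.
- (d) Levels 3 to 7 and missing not improved, [15, 15; 9, 21]: X² = 60 × 180² / (30 × 30 × 24 × 36) = 2.500, p = 0.11.

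**Step 4. Percentages.** With missing excluded, improved is 15/25 = 60% against 9/25 = 36% under both (a) and (c). Not improved is 1/25 = 4% in each arm under (a), but 10/25 = 40% against 16/25 = 64% under (c). Under (a) the two rows add to only 64% and 40%.

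**Step 5. Range.** Hold 15 and 9 improved of 25 and let the much-worse count vary from 0 to 2 per arm, not both 0. The p-value in (a) then runs from 0.086 (0 BID, 2 QD) to 0.89 (2 BID, 1 QD); (c) stays at 0.089. With 0 in both arms, (a) has no test. If the true share much or very much worse is 2%, 5% or 10%, the chance that the not-improved group is empty among 50 graded patients is 0.98⁵⁰ = 36%, 0.95⁵⁰ = 8% or 0.90⁵⁰ = 0.5%.

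**The case against.** The strongest reply is that the intent is clear. Sorting patients into improved and not improved implies a complete split, and a sensible programmer would put levels 3 to 5 in not improved. That is probably what was meant. It is not what 12.4.3 says, and it says it for both scales.

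A reader might infer that levels 3 to 5 also leave the percentage denominator, which would raise improved to 15/16 = 93.8% against 9/10 = 90.0%. The documents do not support this. SAP 6.2 and Appendix 2 make the analysis population the default denominator, and 12.4.3 removes only missing ratings. The improved percentages therefore do not move with the classification gap.

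A reader might also infer from 30 randomized and 25 completers that at most 5 ratings per arm can be missing. Those are approximate planning figures and not a cap, and a completer can also lack a rating.

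Counting missing as not improved is a defensible responder rule, and the SAP sets no precedence between text and table. That stands: the documents show a contradiction, not which rule is right. In the illustration the choice matters little once the groups are complete (p = 0.089 against 0.11).

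The stakes are low, and that stands too. Neither scale is in the endpoint lists of Protocol 11.2.1 or SAP 2, SAP 6.4 plans no formal tests, and no confidence interval is planned for this split.

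**Conclusion.** Both defects are in the text and depend on no assumed number. The split as written gives a wrong two-group chi-square and understates the not-improved percentage. Table 12.5 conflicts with 12.4.3 and 6.3 on missing ratings, misnames the scale in the PGI-I row, and introduces LOCF that 6.3 rules out.

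The sizes (0.73 against 0.089; 4% in each arm against 40% and 64%) rest wholly on assumed counts and show only that the reading can drive the result. The effect is confined to an additional analysis of an 'Other' endpoint with nominal p-values. The seven-category tables still report levels 3 to 5 in full, and the SALT endpoints are unaffected, so nothing here bears on the primary comparison. It should be corrected before unblinding, as a wording and consistency fix.

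**What to change.** - In SAP 12.4.3, for both CGI-I and PGI-I, define not improved as every non-missing answer at levels 3 to 7.
- State one missing-rating rule in both 12.4.3 and table 12.5. Exclusion at that visit, with patients graded at the visit as the denominator, is the rule that 12.4.3 and 6.3 already share. Missing as not improved can be shown as a sensitivity analysis.
- Key the PGI-I row of table 12.5 to a missing PGI-I.
- Remove LOCF from the CGI-I, PGI-S and PGI-I subgroup entries, so that they match the CGI-S entry and 6.3.

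The cost is SAP wording and derivation code. No new data are needed and trial conduct does not change.
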